5.2.11.4. Laboratory Measures – Insulin Antibodies

At each visit (baseline, visits 4, 6, 12, and 24-week (last observation carried forward [LOCF])), total insulin antibody status and its level of total percent binding will be collected. The lower limit of detection of total insulin antibodies is 1.19%. If antibodies are detected then cross reactive antibody status and its level of cross-reactive percent binding will be recorded. The lower limit of detection of cross-reactive antibodies is 1%.

Descriptive and inferential analyses will be performed for the set of FAS patients with a valid antibody testing (detected or ND) at baseline and at least one post baseline visit.

The proportion of patients with detected insulin antibodies will be summarized as counts and percentages at baseline, at each visit, at the 24-week endpoint (LOCF), and overall for the 24-week treatment period. At each of these time points, the proportion of patients with detected antibodies will be compared between treatment groups using Fisher's exact test. These analyses will be performed for patients with antibody levels detectable at baseline and for patients without detectable levels at baseline) in the FAS population.

In addition, the following listing will be provided for patients with detectable insulin antibodies at any time during the study: a listing of level of total insulin antibody percent binding across visits sorted by treatment and maximum postbaseline percent binding in descending order. Similar listings sorted by baseline percent binding as well as by endpoint percent binding will be provided. These listings will be provided for the FAS population.

The level of detectable insulin antibodies (expressed as percent binding) will be summarized by descriptive statistics (mean, median, SD, Q1, inter-quartile range (IQR), Q3, standard error, minimum, and maximum) at baseline, each visit, and endpoint (LOCF). At each of these time points, the median level of percent binding will be compared between treatment groups using the

Wilcoxon rank sum test. Graphical displays of median percent binding and IQR at each visit and endpoint (LOCF) by treatment will be presented. These analyses will be performed for the FAS population, for patients with antibody levels detectable at baseline and without detectable levels at baseline.

All of the analyses above will be performed for the level of cross-reactive antibodies as well.

The treatment-emergent antibody response (denoted TEAR throughout this SAP) is based on the change from baseline to post-baseline in the anti-insulin antibody level (percent binding). TEAR can be sub-classified as either treatment-induced (not detected anti-insulin antibody at baseline) or treatment-boosted (detected anti-insulin antibody at baseline):

- treatment-induced response: change from not detected anti-insulin at baseline to post-baseline detected anti-insulin;
- treatment-boosted response: change from detected anti-insulin at baseline to post-baseline detected anti-insulin antibody level (percent binding) at least 147% of the baseline value.

The number and proportion of patients who have a treatment-emergent antibody response (TEAR) will be summarized by treatment at each post-baseline visit, at the 24-week endpoint (LOCF), and overall for the 24-week treatment period, then analyzed using Fisher's exact test or Pearson's chi-square test.

For patients with TEAR, a visit-wise listing of total and cross-reactive insulin antibody percent binding and clinical outcomes (HbA_{1c}, total hypoglycemia rate, basal insulin dose (U/Day, U/kg/Day) will be presented. The listing will be sorted by treatment and endpoint total insulin percent binding.

Incidence tables showing the number and percent of patients with initial and continuing TEAR at each visit will be presented. Similar analyses will be performed for the detection of total insulin antibodies and for the detection of cross reactive insulin antibodies.

Box plots of clinical outcomes (HbA_{1c}, total hypoglycemia rate, basal dose) will be generated by treatment and TEAR status.

In addition, the following patient listings of insulin antibodies (percent binding) will be provided for patients with TEAR: a listing of level of total insulin antibody percent binding across visit sorted by treatment and maximum postbaseline percent binding; a listing of level of total insulin antibody percent binding across visit sorted by treatment and endpoint percent binding. Similar listings will be presented for cross reactive percent binding.

In addition, the potential impact of total insulin antibody level and TEAR status on clinical response will be evaluated in several ways:

1. The relationship between the natural logarithm of the last observed insulin antibody levels ($\text{Ln}[\text{antibody level}]$) and selected clinical response variables (efficacy and safety measures (eg HbA_{1c}, total hypoglycemia rate, basal dose [U/day, U/kg/day],) will be evaluated using scatterplots and analyzed using ANCOVA on efficacy/safety

measure as the dependent variable with treatment, and entry use of insulin scretagogue (SU, meglitinide, neither) as fixed effects; baseline HbA_{1c} value, baseline response variable, Ln(antibody level) and treatment-by-Ln(antibody level) interaction as covariates for the FAS patients with detectable antibodies postbaseline and with valid antibody testing at baseline (detected, ND). A significant treatment-by-insulin antibody interaction may be indicative of a differential treatment effect necessitating further exploration to determine the nature of the interaction. Only patients with non-missing baseline value and at least one non-missing post-baseline value of the clinical response variable will be included in the analysis.

2. The relationship between TEAR and selected clinical response variables (efficacy and safety measures (e.g. HbA_{1c}, total hypoglycemia rate, basal dose [U/day, U/kg/day],) will be analyzed using ANCOVA on efficacy/safety measure as the dependent variable with treatment, TEAR (yes/no), entry use of insulin scretagogue (SU, meglitinide, neither), treatment-by-TEAR interaction as fixed effects, baseline response variable and baseline HbA_{1c} value as a covariate for the FAS patients with detectable antibodies postbaseline and with valid antibody testing at baseline (detected, ND). A significant treatment-by-TEAR interaction may be indicative of a differential treatment effect necessitating further exploration to determine the nature of the interaction. Only patients with non-missing baseline value and at least one non-missing post-baseline value of the clinical response variable will be included in the analysis.
3. The relationship between TEAR and overall incidence of categories of adverse events (TEAE, SAE, TEAE related to study drug, special topic allergic reactions, injection site reactions) will be assessed by showing the proportion of patients with an event for TEAR and non-TEAR patients by treatments for the FAS. For patients with and without TEAR, treatments will be compared using the Mantel-Haenszel test and the odds ratio and p-value from this test will be reported. The homogeneity of the odds ratios for TEAR and non-TEAR patients will be assessed using the Breslow-Day test.

The potential impact of cross-reactive antibody formation on clinical response similar to the analyses above will be done if there is sufficient number of patients with cross-reactive antibodies.

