LY2963016 is a highly similar version of Lantus® (insulin glargine [rDNA origin] injection), the reference medicinal product (also referred to as the innovator product) produced by Sanofi-Aventis (Lantus® is a registered trademark of Sanofi-Aventis). The primary amino acid sequence of LY2963016 is the same as that of the active ingredient in Lantus®. Both LY2963016 and Lantus® have similar formulations. The clinical development program for LY2963016 has generated evidence substantiating the similar nature in terms of clinical pharmacokinetics and pharmacodynamics, safety, and efficacy of LY2963016 and Lantus®. Study I4L-MC-ABEC was a phase 3, double-blind, 24-week trial to compare the efficacy and safety of LY2963016 to Lantus® in patients with T2DM. The study demonstrated LY2963016 was noninferior to Lantus®. Lantus® was also noninferior to LY2963016. Thus, LY2963016 and Lantus® were considered to have equivalent efficacy. Severe hypoglycemia was the most frequently reported serious adverse event (SAE; LY2963016: 2 patients [0.5%]; Lantus®: 3 patients [0.8%]). There were no statistically significant differences between treatment groups for the overall incidence and overall rate of each category/subcategory of hypoglycemia. There

were no statistically significant differences between treatment groups for the incidence of treatment-emergent adverse events (TEAEs) at the preferred term level. There were no statistically significant treatment differences for the proportion of patients with detectable insulin antibodies (post-hoc analysis) at endpoint (last-observation-carried-forward or last post-baseline observation carried forward [LOCF]) or overall, or for the proportion of patients that developed a treatment emergent antibody response (TEAR) at endpoint (LOCF) or overall. The safety profiles for LY2963016 and Lantus® were similar; there were no new safety findings in either treatment group. The data from this trial demonstrate that LY2963016 provides a well-tolerated and effective once daily (QD) basal insulin option for treatment of patients with T2DM in combination with oral antihyperglycemic medications (OAMs), with an efficacy and safety profile similar to that of Lantus® (insulin glargine).

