4.2. Secondary Objectives

The secondary objectives of the study are as follows:

- To test the hypothesis that Lantus[®] is noninferior to LY2963016 (QD), as measured by change in HbA1c from baseline to 24 weeks, when used in combination with OAMs. (this secondary objective is tested with a gated approach).
- To compare safety of LY2963016 relative to Lantus[®] (proportion of patients with detectable anti-glargine antibodies, hypoglycemia, and injection site reaction) when used in combination with OAMs.
- To compare change in HbA1c at 4, 8, 12, 16, and 20 weeks between LY2963016 and Lantus[®] when used in combination with OAMs.
- To compare 7-point self-monitored blood glucose (SMBG) profiles (as plasma equivalent values) at 0, 2, 6, 12, and 24 weeks between LY2963016 and Lantus[®] when used in combination with OAMs.
- To compare percentage of patients with HbA1c <7% and percentage of patients with HbA1c ≤6.5% at 4, 8, 12, 16, 20, and 24 weeks between LY2963016 and Lantus[®] when used in combination with OAMs.
- To compare LY2963016 to Lantus[®] when used in combination with OAMs with regard to the following measures:
 - inpatient blood glucose (BG) variability
 - basal insulin dose
 - weight change
- To compare LY2963016 relative to Lantus[®] for patient-reported outcomes (PRO) as measured by responses to the Insulin Treatment Satisfaction Questionnaire (ITSQ).

5. A Priori Statistical Methods

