5.2.11.1.2. Assessment of Injection Site Adverse Events

Whenever an injection site adverse event occurs, there is an evaluation of the pain, pruritus, and rash associated with the injection as well as of the characteristics of the injection site (abscess, nodule, lipatrophy, lipohypertrophy, or induration). The proportion of patients experiencing treatment emergent injection site adverse events will be summarized and analyzed by treatment group. Additional analyses will be done as deemed appropriate.

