 - treatment-emergent adverse events (TEAEs) (overall incidence and preferred terms with >5% incidence)
 - TEAEs related to study drug (overall incidence)
 - special topic assessment of allergic events (overall incidence)
 - injection site reactions (overall incidence)
 - serious adverse events (overall incidence)

For rates and incidence of hypoglycemia (total, nocturnal) and categories of adverse events, the same set of 8 subgroups used to analyze change in HbA1c and change in weight will be analyzed.

For each categorical safety outcome and subgroup listed above, the proportion of patients with an event will be compared between treatments for the FAS. Within each subgroup, treatments will be compared using the Mantel-Haenszel test and the odds ratio and p-value from this test will be reported. The homogeneity of the odds ratios across subgroups will be assessed using the Breslow-Day test.

For the 8 subgroups listed above, the rate of total, severe or nocturnal hypoglycemia per year at the 24-week endpoint and for the overall 24-week period will be analyzed. Within each subgroup, treatments will be compared using the negative binomial (NB) model with treatment as the only factor. The NB mean for each treatment and their ratio with corresponding 95% confidence interval will be presented. Additionally, within each subgroup the rates will be compared using the Wilcoxon test. The significance of the subgroup-by-treatment interaction will be evaluated using a negative binomial model with factors treatment, subgroup and treatment-by-subgroup interaction. The negative binomial model will be implemented using the SAS PROC GENMOD with natural logarithm of exposure time (in days) as an offset variable. The above subgroup analysis will be performed and p-values will be provided if there are at least a total of 20 events in the combined treatment groups.

For TEAR at 24 weeks endpoint and overall, subgroup analyses will be performed only for entry age (>65, ≤65) and renal function. For detectable antibodies at 24 weeks endpoint and overall, we will not do subgroup analyses.

Other subgroup analyses may be performed if deemed appropriate as exploratory analyses.

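### The overall comparisons of antibodies, TEAR, allergic events and injection-site events are tests of no difference, with no between-arm difference or confidence interval specified

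*SAP*

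**What the plan says.** SAP 4.2 lists as a secondary objective "To compare safety of LY2963016 relative to Lantus", and names the outcomes as "proportion of patients with detectable anti-glargine antibodies, hypoglycemia, and injection site reaction". The overall between-arm analyses are these:

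- **Detected antibodies (SAP 5.2.11.4).** Counts and percentages at each time point and overall; then "the proportion of patients with detected antibodies will be compared between treatment groups using Fisher's exact test". The analysis set is the "set of FAS patients with a valid antibody testing (detected or ND) at baseline and at least one post baseline visit".
- **TEAR (SAP 5.2.11.4).** Number and proportion by treatment, "then analyzed using Fisher's exact test or Pearson's chi-square test".
- **Allergic events (SAP 5.2.11.1.1).** Counts and percentages, with a Fisher or chi-square comparison.
- **Injection-site events (SAP 5.2.11.1.2).** The proportion with treatment-emergent "injection site adverse events will be summarized and analyzed by treatment group". This section names no test. Fisher or chi-square comes from Protocol 12.2.9.3 and from the SAP 5.2.1 default for categorical measures.

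SAP 5.2.1 sets confidence intervals at two-sided 95% but ties them to no safety proportion. Effect measures for these outcomes appear only in breakdowns. SAP 5.2.12 says that within subgroups "treatments will be compared using the Mantel-Haenszel test and the odds ratio and p-value from this test will be reported", and SAP 5.2.11.4 does the same for adverse-event categories by TEAR status. Neither names a CI for the odds ratio. SAP 5.2.12 also says that detectable antibodies will have no subgroup analysis, so that outcome has no effect measure anywhere.

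**The concern.** LY2963016 is presented as highly similar to its reference. For HbA1c the plan handles this properly: equivalent efficacy is judged from a confidence interval against ±0.4%. The safety proportions have no counterpart. A test of no difference yields a p-value, which does not say how large an excess on LY2963016 the data still allow. If the test is not significant, a reader of the report cannot tell from it whether a sizeable excess has been excluded or simply not detected.

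The plan is also uneven. It promises an odds ratio for injection-site and allergic events within subgroups, but no effect measure for the overall comparison that answers the objective. Overall hypoglycemia is better placed, because it has logistic and negative binomial models; it is not part of this point.

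**Working it through.** **1. What the sample size was built for (SAP 5.1).** Inputs: margin 0.40, SD 1.3, true difference 0, two-sided 0.05, 450 completers at 2:1 (300 and 150), 15% dropout.

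- SE = 1.3 × √(1/300 + 1/150) = 1.3 × 0.10 = 0.13.
- Power = Φ(0.40/0.13 − 1.96) = Φ(1.117) = 86.8% (86.7% with the t distribution). This agrees with the stated figure of over 85%.
- 450/0.85 = 529.4, so 530 randomized (353 and 177), as stated.

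The plan's figures reproduce. They concern HbA1c alone; no power or detectable difference is given for any safety proportion.

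**2. What the Fisher test would miss.** Alpha is 0.05 two-sided (SAP 5.2.1). The documents give no antibody, TEAR or injection-site rates, so every rate below is an assumption. The miss rate is 1 − power, from exact enumeration of all 2×2 tables, with the higher rate on LY2963016. The 300 vs 150 column shows the effect of fewer evaluable patients, since the antibody set requires valid baseline and post-baseline tests.

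| Assumed Lantus vs LY2963016 | Missed, 353 vs 177 | Missed, 300 vs 150 |
|---|---|---|
| 2% vs 4% | 82.4% | 85.7% |
| 3% vs 6% | 71.9% | 76.8% |
| 5% vs 10% | 50.7% | 57.9% |
| 10% vs 15% | 66.9% | 70.9% |
| 10% vs 20% | 15.5% | 21.8% |
| 15% vs 30% | 2.8% | 5.4% |
| 20% vs 30% | 32.0% | 38.5% |
| 30% vs 40% | 40.6% | 46.5% |
| 30% vs 45% | 8.7% | 13.5% |

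At the full size the miss rate runs from about 3% to 82%, depending on the pair. Large excesses would usually be found; modest ones often would not.

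**3. What an interval would show.** With equal true rates p, the approximate (Wald) 95% half-width for the risk difference is 1.96 × √[p(1 − p)(1/353 + 1/177)]. At p = 10% this is 1.96 × √(0.09 × 0.00848) = 5.4 points.

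| Assumed common rate | Half-width, 353 vs 177 | Half-width, 300 vs 150 |
|---|---|---|
| 3% | 3.1 points | 3.3 points |
| 10% | 5.4 points | 5.9 points |
| 20% | 7.2 points | 7.8 points |
| 30% | 8.3 points | 9.0 points |

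So with equal observed rates of 20%, the interval would exclude an excess above about 7 points. A p-value does not convey that.

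**The case against.** The strongest reply is that the plan never claims to show safety similarity. The objective is to compare safety, and the equivalence conclusion is reserved for efficacy. This is right. A reader might infer that non-significance will be read as similarity, because Protocol Section 5 reports of the earlier study that "There were no statistically significant treatment differences for the proportion of patients with detectable insulin antibodies" and then describes the safety profiles as similar. But that is a background account of a completed trial. It is not a decision rule for this one, and no section of either document supplies such a rule.

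A second reply is that the antibody analysis is much richer than one p-value. The SAP also plans percent-binding summaries with Wilcoxon tests, plots, results by baseline antibody status, TEAR incidence tables, and models relating antibodies and TEAR to HbA1c, hypoglycemia and dose. Counts by arm let a reader work out a difference and its interval. This also stands, but those analyses answer other questions, and an interval left to the reader is not prespecified.

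A third reply is that the miss rates depend on the rates chosen. That is so. For 20% vs 30% and 30% vs 40%, detection is more likely than not. A narrower range of miss rates should not be quoted as a property of the plan.

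Finally, an interval without a margin still leaves a judgement. It does, but the judgement then rests on a visible range of differences.

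**Conclusion.** The gap is real but limited. For four outcomes under the safety analyses, two of them named in a secondary objective, the plan specifies counts, percentages and a test, but no overall between-arm difference with an interval. The general CI sentence and the stratified odds ratios do not fill it. That finding rests on the text alone and needs no assumed event rate.

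The size of the problem does depend on assumptions. A Fisher test in a trial sized for HbA1c would miss modest excesses often and large ones seldom, as tabulated; the true rates are unknown from the documents.

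Two further readings are not supported. Neither document ranks immunogenicity above hypoglycemia or injection-site reactions as the main safety comparison. Neither says what excess would count as a relevant harm, and detectable antibody is a laboratory finding whose clinical bearing the SAP examines separately. The primary and gated HbA1c analyses are unaffected.

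**What to change.** In SAP 5.2.11.4, 5.2.11.1.1 and 5.2.11.1.2, add the LY2963016 minus Lantus risk difference with a two-sided 95% CI (for example Miettinen-Nurminen) for:

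- detected antibodies, at the 24-week endpoint and overall;
- TEAR, at the 24-week endpoint and overall;
- allergic events;
- injection-site adverse events.

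Add a statement that p > 0.05 will not be taken as evidence of similarity for these outcomes, and that the interval will be used to describe which excess on LY2963016 is excluded. Keep Fisher's test as descriptive, and name it in 5.2.11.1.2, which at present names no test.

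The cost is SAP wording, to be settled before database lock, and one added column in tables already planned. No margin, new data or extra patients are needed. The drawback is that the report will show fairly wide intervals, with half-widths of about 5 to 8 points at assumed rates of 10% to 30%. These look less favourable than a bare non-significant p-value.

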Unless otherwise noted, all tests of treatment effects will be conducted at a 2-sided alpha level of 0.05, and confidence intervals (CIs) will be calculated as 2-sided 95% CIs. All tests of interactions between treatment groups and other factors will be conducted at a 2-sided alpha level of 0.05. No adjustments for multiplicity will be performed. See Section 5.2.7 for the gate-keeping strategies used for primary/secondary endpoints.

The baseline is Visit 2. If baseline data are missing, the last measurement taken prior to this visit will be used for the baseline measurement.

The last visit for the 24-week treatment study is Visit 18. If the Visit 18 measurement is missing, the last post-baseline value will be carried forward to create the 24-week endpoint value using the last-observation-carried-forward (LOCF) methodology. If there are no measurements after Visit 2 (date of randomization), the 24-week endpoint values will be considered missing. Efficacy analyses only be conducted for patients with both nonmissing baseline value and at least 1 nonmissing post-baseline value.

The LOCF methodology will be utilized in the endpoint analyses using analysis of covariance (ANCOVA) of HbA_{1c}, laboratory chemistry and hematology, as well as analysis of hypoglycemia (rate and incidence) and insulin antibodies.

Unless otherwise noted, the analysis of the continuous secondary efficacy and safety measurements (SMBG at each time point and summaries of SMBG, weight, dose, and vital signs) will use the same mixed model repeated measure (MMRM) methodology for the primary efficacy analyses with the baseline value of the response variable as a covariate with the FAS patient population. Continuous laboratory measures will be analyzed using an analysis of covariance (ANCOVA) model.

For categorical measures, Fisher's exact test will be used. To avoid computational problems, a maximum computation time of five minutes will be programmed into the analysis for Fisher's exact test. If it does not converge in that time, the Pearson's Chi-square test will be utilized.

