5.2.11.2. Hypoglycemic Events

A **hypoglycemic episode** is that at any time a patient feels as he/she is experiencing a sign or symptom that is associated with hypoglycemia or has a BG level of ≤ 70 mg/dL (≤ 3.9 mmol/L), even if it was not associated with signs, symptoms, or treatment.

Severe hypoglycemia: an event requiring assistance of another person to actively administer carbohydrates or glucagon or take other corrective actions. Plasma glucose concentrations may not be available during an event, but neurologic recovery following the return of plasma glucose to normal levels is considered sufficient evidence that the event was induced by low plasma glucose concentration.

Nocturnal hypoglycemia: any total hypoglycemic event that occurs after bedtime and prior to the first meal upon waking (eg, breakfast).

Documented symptomatic hypoglycemia: an event during which typical symptoms of hypoglycemia are accompanied by a measured plasma glucose concentration ≤ 70 mg/dL (≤ 3.9 mmol/L).

Asymptomatic hypoglycemia: an event not accompanied by typical symptoms of hypoglycemia but with a measured plasma glucose concentration ≤ 70 mg/dL (≤ 3.9 mmol/L).

Probable symptomatic hypoglycemia: an event during which symptoms typical of hypoglycemia are not accompanied by a plasma glucose determination but that was presumably caused by a plasma glucose concentration ≤ 70 mg/dL (≤ 3.9 mmol/L).

Besides the hypoglycemic categories listed above, total hypoglycemic event will be defined as follows:

Total hypoglycemic event: any event which is either documented symptomatic hypoglycemia, asymptomatic hypoglycemia, probable symptomatic hypoglycemia or severe hypoglycemia.

For each category of hypoglycemia event, the incidence, the number of hypoglycemic events per patient, the rate of hypoglycemic events per year (that is, the number of hypoglycemic episodes per patient per patient year [365.25 days]) will be calculated. These measures will be summarized at baseline, titration, maintenance, and overall study periods and at endpoint.

The proportion of patients with at least 1 hypoglycemic event (total, severe, nocturnal, and others) or incidence during the study will be summarized (counts and percentages) and analyzed using Fisher's exact test or the Pearson's chi-square test for the FAS population.

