Logistic regression will be used as a sensitivity analysis of the incidence of hypoglycemia. The model will have presence or absence of hypoglycemia as the dependent or response variable and treatment, baseline HbA_{1c}, and entry use of insulin scretagogue (SU, meglitinide, neither) as the independent terms in the model.

The rate of hypoglycemic episodes per year (total, severe, nocturnal, and others) will be analyzed at baseline, titration, maintenance, and overall study periods and at endpoint using the Wilcoxon test. In addition, the hypoglycemia rates will also be analyzed using a negative binomial model for the FAS population with terms for treatment, baseline HbA_{1c}, and entry use of insulin scretagogue (SU, meglitinide, neither).

In addition, the total number of patients with at least 1 hypoglycemic episode divided by the total extent of exposure in patient-years will be calculated for the overall study period and summarized descriptively for each treatment group for total, severe, nocturnal, documented symptomatic, asymptomatic hypoglycemia and probable symptomatic hypoglycemia. Individual patient listing of hypoglycemic events by visit will be presented for the FAS population.

All the above analysis will be repeated with the threshold of **Clinically significant hypoglycemia:** < 54 mg/dL (3.0 mmol/L) for hypoglycemia categories of total hypoglycemia,

nocturnal hypoglycemia, documented symptomatic hypoglycemia and asymptomatic hypoglycemia.

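### The antibody impact analyses fit ANCOVA to the total hypoglycemia rate, which the rest of the plan models as negative binomial; if antibody level affects hypoglycemia, the treatment-by-Ln(antibody) test can exceed its nominal 5%

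*SAP*

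**What the plan says.** SAP 5.2.11.4 ends with numbered analyses of whether antibodies affect clinical response. Item 1 uses the natural log of the last observed antibody level: "total hypoglycemia rate, basal dose [U/day, U/kg/day],) will be evaluated using scatterplots and analyzed using ANCOVA". Item 2 uses TEAR: "total hypoglycemia rate, basal dose [U/day, U/kg/day],) will be analyzed using ANCOVA on efficacy/safety measure as the dependent variable". Both adjust for secretagogue use, baseline HbA1c and the baseline value of the response, and both include an antibody-by-treatment interaction. No transformation, weighting, offset or count model is given for the hypoglycemia rate.

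On item 1, the SAP adds: "A significant treatment-by-insulin antibody interaction may be indicative of a differential treatment effect necessitating further exploration to determine the nature of the interaction". Item 2 carries a parallel sentence for TEAR. The level comes from SAP 5.2.1: "All tests of interactions between treatment groups and other factors will be conducted at a 2-sided alpha level of 0.05".

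SAP 5.2.11.2 defines the rate as "the number of hypoglycemic episodes per patient per patient year [365.25 days". It analyzes the rate first by Wilcoxon test and then adds: "In addition, the hypoglycemia rates will also be analyzed using a negative binomial model for the FAS population". That section does not state an offset. SAP 5.2.12 does: its negative binomial model has log exposure in days as offset and includes a treatment-by-subgroup interaction. Protocol 12.2.9.4 also pairs the negative binomial model with log-duration offsets.

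**The concern.** HbA1c and insulin dose suit ANCOVA. The hypoglycemia rate does so less well, for three reasons.

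- **Precision.** Each patient's rate counts equally, whether it rests on two weeks of follow-up or twenty-four.
- **Variance.** The variance of a count-based rate rises with its mean. If the mean depends on antibody level, the ordinary standard error of the interaction is wrong.
- **Scale.** ANCOVA treats effects as additive. If antibodies multiply the rate equally in both arms and the arms' rates differ, an additive interaction appears although the rate ratio is constant.

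At stake is a false antibody-by-treatment safety signal in a comparison of two highly similar insulins, which would then have to be explained after the data are seen.

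**Working it through.** **The plan's own figure.** The documents give no size or power for the antibody analyses. The only design calculation is for HbA1c, and it reproduces. SE = 1.3 × √(1/300 + 1/150) = 0.130; 0.40/0.130 − 1.96 = 1.117; power = 86.8%, in line with the stated power of over 85%. Also, 450/0.85 = 529.4, so 530 randomized. This point does not rest on that calculation.

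**Inputs from the documents.** 2:1 allocation, 24 weeks (168 days), 15% dropout, interaction alpha 0.05 two-sided.

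**Assumptions, not in the documents.** Base rate 5 per patient-year; negative binomial dispersion k = 1 or 2; SD of Ln(antibody) 0.8; TEAR in 50%; 60 to 250 patients with detectable antibodies; no other covariates.

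**Unequal precision.** One event in 14 days gives 365.25/14 = 26.1 per year. Twelve events in 168 days give 12 × 365.25/168 = 26.1 per year. ANCOVA weights them alike. For a true rate λ over t years, the variance of the observed rate is λ/t + kλ². With λ = 5 and k = 1:

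- 14 days (t = 0.0383): 130.4 + 25 = 155.4
- 168 days (t = 0.460): 10.9 + 25 = 35.9, so the short record is 155.4/35.9 = 4.3 times as variable.

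**Variance rising with the mean.** Doubling the rate to 10 over 168 days gives 21.7 + 100 = 121.7, which is 121.7/35.9 = 3.4 times the variance.

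**Scale.** With base rate 5, arm ratio 1.5, antibody ratio 2 and no ratio interaction, the four means are 5, 7.5, 10 and 15. The additive interaction is 15 − 10 − 7.5 + 5 = 2.5 per year. With arm ratio 1.0 the means are 5, 5, 10 and 10, and it is 0.

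**Simulation of the item 1 interaction test.** No interaction on the rate-ratio scale; ANCOVA on count/exposure; 4,000 replicates per setting (Monte Carlo SE at 5%: √(0.05 × 0.95/4000) = 0.3 points). Entries are rejection rates in % for k = 1 / k = 2; a dash means not run in this set.

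| Arm ratio | Antibody ratio per Ln unit | N = 60 | N = 100 | N = 250 |
|---|---|---|---|---|
| 1.0 | 1.0 | 4.7 / 5.2 | 4.8 / 4.9 | 4.5 / 5.4 |
| 1.0 | 1.5 | 7.1 / 7.4 | 7.0 / 7.9 | 7.5 / 8.3 |
| 1.0 | 2.0 | 10.9 / 10.1 | 13.1 / 12.7 | 14.9 / – |
| 1.5 | 1.5 | 6.0 / 4.8 | 7.2 / 4.7 | – |
| 1.5 | 2.0 | 10.8 / 7.7 | 14.1 / 12.0 | – |

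Further runs at k = 1 with arm ratio 1.5 and antibody ratio 2 gave 15–27%.

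**Item 2 (binary TEAR).** ANCOVA rejects in 2.5–5.4% of runs at N = 60 to 100. It reached about 9% only at N = 250 with both effects large.

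**Negative binomial with ln(exposure) offset.** Across the completed settings (500 replicates, SE about 1 point) it rejects in 3.8–7.8% of runs. At N = 100 with arm ratio 1.5 and antibody ratio 2 per Ln unit, it rejects in 4.4–6.0%, against 12.0–14.1% for ANCOVA.

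**The case against.** The strongest reply is that little hangs on these tests. They are supportive, with no decision rule. A significant interaction only prompts exploration, and the SAP already plans scatterplots, box plots by treatment and TEAR status, and patient listings. That stands and keeps the point minor, but the displays do not correct the test.

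A reader might infer that every such interaction is an artefact of scale. The documents do not support that. The scale mechanism needs the arms' rates to differ. The protocol's introduction reports no significant differences in hypoglycemia rates in the earlier type 2 trial. With equal arms the inflation comes from unequal variance: a robust (HC3) standard error brings the N = 100 figures at an antibody ratio of 2 back to 4.6–4.8%. That simpler remedy is not enough if the arms do differ; at arm ratio 1.5 it still leaves 11.3% and 8.6%. An interaction on the rate-difference scale is also a legitimate quantity, and the SAP does not commit to the rate ratio alone, since the Wilcoxon test comes first in 5.2.11.2.

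Two other inferences fail. Items 1 and 2 are not equally affected: TEAR shows no general inflation. Nor does ANCOVA ignore follow-up: the rate is already divided by exposure, so what remains is unequal precision.

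Finally, the larger figures need a doubling of the rate per Ln unit, for which the documents give no source. That also stands.

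**Conclusion.** The concern holds in limited form. Items 1 and 2 use a model that fits the hypoglycemia rate poorly and departs, without a stated reason, from the model used for it elsewhere in the plan.

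For item 1, if antibody level is related to hypoglycemia, the interaction test can exceed 5%. With equal arms it is about 7–8% at a rate ratio of 1.5 per Ln unit, and 13–15% at a ratio of 2 with 100 to 250 patients (10–11% with 60). An arm difference on top can add to this when the antibody effect is strong, but it adds little in small subsets. With equal arms and no antibody effect, size is 4.5–5.4%.

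For item 2 the grounds are mainly unequal precision and consistency. All sizes rest on the assumed rate, dispersion, antibody spread and subset size, and were obtained without the SAP's other covariates. Nothing here touches the primary noninferiority conclusion.

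**What to change.** In SAP 5.2.11.4, items 1 and 2, for the hypoglycemia response only, replace ANCOVA with a negative binomial model of each patient's event count. State the ln(exposure) offset explicitly, because SAP 5.2.11.2 does not. Keep every term the items already list: treatment, secretagogue use, baseline HbA1c, baseline hypoglycemia response, the Ln(antibody) or TEAR term, and its interaction with treatment. Report rate ratios with likelihood-ratio tests. Keep ANCOVA for HbA1c and basal dose.

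The cost is a wording change and some programming, since none of the planned negative binomial models contains an antibody term. The model may fail to converge in a small antibody-positive subset.
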